#### 4 Case selection

##### 4.1 Chikungunya fever diagnostic criteria

Suspected or confirmed cases of Chikungunya fever were included based on the diagnosis criteria of Chinese Guidance of the Diagnosis and Treatment for Chikungunya Fever (2017 Edition) published by the Chinese Center for Disease Control and Prevention.

###### 4.1.1 Basis of diagnosis

- 1) Epidemiological data: living in Chikungunya fever endemic areas or having a travel history to epidemic areas within 12 days, and having a history of mosquito bites within 12 days before onset of the disease.
- 2) Clinical manifestations: Acute onset, with fever as the first symptom, rash appears 2 to 5 days after the disease, and severe pain in multiple joints.
- 3) Lab assessment: Chikungunya RNA detection from patient blood samples.

###### 4.1.2 Diagnostic criteria

- 1) Suspected diagnosis: patients with the above-mentioned epidemiological history and clinical manifestations; or patients without epidemiological history but with the above-mentioned typical clinical manifestations.
- 2) Confirm the diagnosis: Patients with positive result of Chikungunya virus nucleic acid.

##### 4.2 Inclusion Criteria

- (1) Meets the suspected or confirmed diagnostic criteria for chikungunya fever;
- (2) Symptom onset  $\leq$  3 days before enrollment;
- (3) Actual prescribed treatment aligns with the study's group assignment (Chinese medicine, Western medicine, or combined therapy);
- (4) Sign the informed consent form.

##### 4.3 Exclusion criteria

- (1) Severe chikungunya fever;
- (2) Participation in another drug clinical trial within the past 3 months;
- (3) Other conditions that the researchers consider unsuitable for inclusion .

#### 4.4 Source of Cases

At each research center, all eligible patients will serve as observation subjects for this cohort study. Patients will be assigned to respective observation cohorts based on their actual prescription status, with enrollment for each group continuing until the target number is reached.

#### 4.5 Withdrawal Criteria

Eligible patients will undergo a 28-day follow-up, or until the occurrence of any of the following events:

- (1) Allergic reactions or serious adverse events (SAEs) that, in the investigator's judgment, warrant discontinuation of observation;
- (2) Severe comorbidities or special pathological changes during the study that, in the investigator's opinion, make continuation inadvisable;
- (3) Post-enrollment discovery of significant protocol violations by the patient;;
- (4) Patient death, loss to follow-up, or voluntary withdrawal.

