#### 4.6 Handling of dropout cases

If a patient drops out, the investigator must document the reason in the eCRF, attempt to contact the patient, complete all feasible assessments, and fill out the end-of-treatment follow-up record. The last medication time should be recorded whenever possible, and follow-up should continue until the study endpoint. If the dropout is due to an adverse event (AE) later judged to be related to the study treatment, this must be recorded in the eCRF.

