## 7.2 Recording of adverse events

The name, severity, time of occurrence, duration, treatment measures, and process of treatment of adverse events, important adverse events, and adverse reactions that occur from the beginning of the treatment period to the last visit should be recorded in the research medical record, and their relevance to the trial drug should be evaluated based on comprehensive consideration of comorbidities and concomitant medications, and recorded in detail by the researcher.

When adverse events or adverse reactions are found, researchers can determine whether to discontinue observation based on the patient's condition. Cases in which medication is discontinued due to adverse events or adverse reactions should be followed up and the results recorded in detail.

If any abnormality is found in the safety test indicators such as vital signs, physical examination, complete blood count, urine routine, liver function, kidney function, electrolytes, etc. during or after treatment, the test must be repeated at an appropriate time and comprehensively analyzed with the subjects' onset and treatment to determine whether it is related to the test drug.

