#### 7.7 Adverse events that were not relieved during follow-up

Adverse events that have not yet resolved at the study endpoint or have not been resolved must be followed up until one of the following events occurs:

- (1) Incident mitigation;
- (2) The event is stable;
- (3) if the baseline value is acceptable, the event returns to the baseline level;
- (4) When it is impossible to obtain additional information (the subject or the person who takes care of him/her refuses to provide additional information, and the subject is lost to follow-up despite follow-up efforts (at least 3 telephone contacts)).

Follow-up methods can be hospitalization, outpatient clinic, home visit, telephone, correspondence, etc.

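### Sections 4.5 and 7.2 let an adverse event end observation, 4.6 says dropouts are followed to the study endpoint, and the protocol does not say which rule governs

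*Protocol*

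**What the plan says.** Three sections of the Protocol decide what happens to a patient who deteriorates.

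- **4.5 Withdrawal Criteria** opens with "Eligible patients will undergo a 28-day follow-up, or until the occurrence of any of the following events". Item (1) is "Allergic reactions or serious adverse events (SAEs) that, in the investigator's judgment, warrant discontinuation of observation". Item (2) is "Severe comorbidities or special pathological changes during the study", where the investigator thinks that going on is inadvisable.
- **7.2 Recording of adverse events** covers any adverse event or reaction, not only serious ones: "researchers can determine whether to discontinue observation based on the patient's condition". Its next sentence adds "Cases in which medication is discontinued due to adverse events or adverse reactions should be followed up".
- **4.6 Handling of dropout cases** asks for the reason, an attempt at contact and all feasible assessments, and then says "follow-up should continue until the study endpoint". Its last sentence treats exits caused by an adverse event as dropouts.

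Section 7.7 says that unresolved adverse events "must be followed up until one of the following events occurs". Section 4.4 forms the cohorts by actual prescription, so the investigator knows the treatment. The remarks on unblinding in 7.5 and 7.6 do not set up any blinding. Section 10 plans Kaplan-Meier estimates and log-rank tests for times to event.

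**The concern.** For one and the same patient, 4.5 and 7.2 allow data collection to end and 4.6 asks for it to go on. The trigger is deterioration, which is related to the outcomes being compared, and the decision is discretionary and made with treatment known. If sites follow 4.5 and 7.2, the patients least likely to recover soon leave the record. Recovery can then look better than it was, and most so in the cohort with most deterioration. The comparison of cohorts that serves objective 2 is non-randomised, so no allocation scheme balances such losses. Data that were never collected cannot be restored by any later analysis rule, which is why the wording matters at the protocol stage.

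**Working it through.** **1. Trace one patient.** Take a patient with an SAE on D3 who is alive, consenting and reachable.

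| Rule | Last outcome data |
|---|---|
| 4.5(1) or 7.2, if the investigator stops observation | D3 |
| 4.6, reading its endpoint as the end of the 28 days | D28, through D5/discharge and the D7, D14 and D28 calls |

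The rules give different data, and no sentence ranks them.

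**2. Do nearby rules settle it?** The follow-up sentence in 7.2 is tied to stopping medication, not observation. Section 7.7 follows the adverse event itself. Neither asks for the symptom scale after observation has stopped. Section 9.1.3 states only a general aim to limit losses.

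**3. What would be lost.** The flow chart schedules the symptom scale to D28, so 6.2(5)-(6) are most exposed. Temperature, RNA, blood counts, CRP for DAS44 and the rash scores on days 3 and 5 are affected only by exits before those time points. Temperature, RNA and blood counts have no scheduled assessment after D5/discharge for anyone.

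**4. Size.** The protocol gives no figure to reproduce, so every input here is an assumption:

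- a share q progresses and has not recovered by day T;
- 80% of the others recover by T at a constant daily rate;
- a share w of progressors, the same in both cohorts, leaves on D3 and is censored then, still counted at risk on D3.

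With A = (1−q)·0.2^(3/T) and B = (1−q)·0.2:

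- Kaplan-Meier recovery by T = 1 − (A+q)·[B+q(1−w)] / [A+q(1−w)]
- True recovery by T = 0.8(1−q)

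Worked case, T = 7 and w = 1, with 0.2^(3/7) = 0.5017:

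- q = 0.02: A = 0.4917, B = 0.196; 1 − 0.5117×0.196/0.4917 = 79.6%, true 78.4%.
- q = 0.01: A = 0.4967, B = 0.198; 1 − 0.5067×0.198/0.4967 = 79.8%, true 79.2%.
- Gap: −0.2 points estimated, −0.8 true.

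Gaps in percentage points, by the same formula:

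| q in the two cohorts | True | D7, all / half withdrawn | D28, all / half withdrawn |
|---|---|---|---|
| 2% v 1% | −0.80 | −0.20 / −0.51 | −0.04 / −0.43 |
| 5% v 2% | −2.40 | −0.60 / −1.56 | −0.11 / −1.31 |
| 10% v 2% | −6.40 | −1.59 / −4.28 | −0.30 / −3.58 |

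At 2% v 1% the distortion is at most 0.80 − 0.04 = 0.76 points. If only 10% to 20% of progressors are withdrawn, the D7 gap is −0.74 to −0.69 for 2% v 1%, and −6.01 to −5.61 for 10% v 2%.

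The level within one cohort moves more than the gap. At q = 2% with all withdrawn, recovery is overstated by 79.6 − 78.4 = 1.2 points at D7 and 79.9 − 78.4 = 1.5 at D28. That is also the spurious gap in the extreme case where one cohort withdraws all its progressors, the other none, and 2% progress in both.

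**5. Why continued contact matters.** Suppose 40% of progressors recover by D28. True recovery is 80×0.98 + 40×0.02 = 79.2% v 80×0.99 + 40×0.01 = 79.6%, a gap of −0.4. If all progressors are withdrawn and counted as not recovered, the result is 78.4% v 79.2%, a gap of −0.8. Only follow-up recovers −0.4.

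**The case against.** The strongest reply is that 4.5 lists who withdraws and 4.6, the next section, says what is then done. On that reading every 4.5 withdrawal is followed on, and harm arises only if a site ignores 4.6. This is the natural order of such sections and probably what was meant. It stands as a reason to rate the point modestly. It does not remove the point, because the opening of 4.5 makes the listed events an end to follow-up, 7.2 speaks of stopping observation, and several centres must apply the text.

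A reader might infer more than the documents support, in three ways.

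- **That the planned analysis is biased by informative censoring.** Section 10 names Kaplan-Meier and log-rank but states no censoring rule. How deterioration and death enter the recovery times is ordinary content of a statistical analysis plan, which is not at hand. The figures above show what would follow if such patients were censored.
- **That the complication rate in 6.2(9) is seriously undercounted.** It counts patients with a recorded listed complication, so a patient withdrawn because of one is already counted. Only a patient withdrawn for another reason who later has a listed complication is missed.
- **That investigators will stop observation more often in one cohort.** The text leaves room for this, but nothing in it shows that it will happen.

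It also stands that severe disease is excluded at entry (4.3), so low progression is plausible and 10% v 2% is an extreme case. The three outcomes in bold in the Program Summary (DAS44, rash, fever) depend little on follow-up after D5/discharge.

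**Conclusion.** The conflict is in the text and should be resolved. The protocol does not order the data of deteriorating patients to be discarded: 4.6 points the other way and is probably the intended rule. The fault is that 4.5 and 7.2, read literally, permit the loss and nothing says that 4.6 prevails.

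The size cannot be known from the protocol. If 80% of non-progressors recover, exits occur on D3, exits are censored and the same share is withdrawn in each cohort, the between-cohort gap is distorted by less than 1 percentage point at 2% v 1% progression. It becomes larger if progression differs markedly between cohorts and many progressors are withdrawn. The case for acting is that the change is cheap and decides which data exist, not that a large bias has been shown.

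**What to change.** Add one sentence to 4.5 and one to 7.2: an SAE, other adverse event or severe change is recorded and may stop treatment, but does not stop observation. Scheduled assessments, including the D7, D14 and D28 calls, continue to D28 as 4.6 says, from hospital records where the patient cannot be assessed directly. Only death, withdrawal of consent or loss to follow-up ends observation. This wording also means that a protocol violation under 4.5(3) no longer ends follow-up; whether such a patient is analysed can be settled at data review.

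The calls are already scheduled, so the cost is the wording and some retrieval of records for patients who are transferred or too ill for the diary or telephone.

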#### 4.6 Handling of dropout cases

If a patient drops out, the investigator must document the reason in the eCRF, attempt to contact the patient, complete all feasible assessments, and fill out the end-of-treatment follow-up record. The last medication time should be recorded whenever possible, and follow-up should continue until the study endpoint. If the dropout is due to an adverse event (AE) later judged to be related to the study treatment, this must be recorded in the eCRF.

#### 4.7 Criteria for case exclusion:

- (1) Violation of inclusion criteria by the patient;
- (2) Absence of any post-enrollment data;
- (3) Joint determination by statisticians and investigators prior to database locking;
- (4) Other criteria to be determined during data review based on actual circumstances.

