## 7.5 Management of adverse events

If adverse events occur to the subjects during the trial, they shall be handled according to the following procedures:

After discovering that a subject has an adverse event, the researcher needs to inquire in detail about the subject's symptoms and signs at the time. If necessary, symptomatic treatment can be given first. The research physician will preliminarily assess the severity of the adverse event and its relevance to the trial drug, and provide further treatment advice:

- ① General adverse events: The outcome of the event can be closely and continuously observed or corresponding symptomatic treatment can be performed;
- ② Important adverse events: The research physician should inform the principal investigator promptly and take measures such as suspending treatment, adjusting drug dosage and providing targeted treatment according to the subject's condition. If necessary, the principal investigator may decide whether to urgently unblind the subject (if applicable).
- ③ Serious adverse events: Handle and report as the following "serious adverse events".
- ④ The research physician will treat the subject according to the condition of the patient. If the subject's injury exceeds the treatment capabilities of the research department, the relevant departments will be consulted and assist in handling the situation.

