### 8.6 Data review

Before the data review meeting, samples will be drawn for quality control according to the ratio specified in the relevant SOP of the Data Management Department for the queries manually closed by the data administrator. If the quality control error rate is within the specified range, then the quality control is passed; if the quality control error rate is not within the specified range, samples will be drawn again for quality control according to the specified ratio. If it still fails, 100% quality control will be performed on all manually closed queries.

After the data cleaning is completed, the sponsor will be notified to hold a data review meeting. The sponsor, principal investigator, data management personnel, and statistician will conduct a final review of unresolved data issues and discuss the data set division according to the data review report.

After all the data are confirmed, the principal researcher will electronically sign the electronic data.

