## 8.7 Locking and unlocking the database

### 8.7.1 Database Lock

Data locking should meet the following prerequisites:

- (1) All data have been collected and data processing such as data entry has been completed.
- (2) All data queries have been answered and the database has been modified based on the data queries.
- (3) If coding is required, ensure that the review of the medical data coding list has been completed to ensure the integrity and consistency of medical coding.
- (4) The final data logic and consistency check has been completed.
- (5) The data quality review has been completed and meets the requirements for statistical analysis.
- (6) All trial related documentation was updated and saved.

After the data manager confirms that the trial meets the above conditions, he/she will submit a written lock application, which will be signed and dated by trial-related personnel (data manager, biostatistician, project manager, sponsor, principal investigator). Once the written approval document for database locking is obtained, the database will be locked.

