## 9.1 Bias Control

### 9.1.1 Selectivity bias control

Mainly in the design and implementation stage. The target population of the program design is accurate, and the hospital and doctor selection ensure the representativeness of the sample cases; once the doctor starts to register, there is no selection of registered cases, etc.

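### Section 4.7(3)-(4) allows enrolled cases to be excluded on unstated grounds settled at an unmasked data review, so exclusions could depend on cohort and response

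*Protocol*

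**What the plan says.** Section 4.7 lists four grounds for excluding a case. The first two are stated in advance: an inclusion criterion was not met, or there are no data after enrolment. The third is "Joint determination by statisticians and investigators prior to database locking", which names who decides and when, but not on what basis. The fourth is "Other criteria to be determined during data review based on actual circumstances".

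Section 8.6 fixes the timing and the participants: "After the data cleaning is completed, the sponsor will be notified to hold a data review meeting". The sponsor, principal investigator, data managers and statistician then settle open data issues and "discuss the data set division according to the data review report". Section 8.7.1 makes it a condition of lock that "All data have been collected and data processing such as data entry has been completed".

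On treatment, section 4.4 says "Patients will be assigned to respective observation cohorts based on their actual prescription status". Section 3 describes a prospective observational design, and section 8.3 has clinicians collect the data. Section 9.1.1 relies, as a control on selection bias, on the statement that "once the doctor starts to register, there is no selection of registered cases".

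**The concern.** Settling analysis sets late is ordinary practice when the people deciding cannot see treatment and outcome. Here the treatment is open, the data are already collected and cleaned, and the grounds for exclusion may be written at the meeting. Nothing in the protocol prevents a decision to drop a case from being influenced by the patient's cohort and course of illness.

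If removal depends on cohort and response together, the retained cohorts differ in response for reasons unrelated to treatment. The methods named in section 9.1.4 (stratification, standardisation, multivariable models, propensity scores) balance measured characteristics among retained patients. They do not recover the outcomes of patients taken out because of those outcomes. The t-tests, analyses of variance, chi-square or Fisher tests and log-rank tests of section 10 would carry the same distortion wherever they are run on the reduced set.

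**Working it through.** **Comparison of the sections**

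1. *Is a criterion stated?* 4.7(1) and 4.7(2): yes. 4.7(3) and 4.7(4): no.
2. *When is it settled?* At data review, after cleaning (8.6) and before lock (4.7, 8.7.1), so outcomes have been collected.
3. *Is the cohort visible?* The cohort is the treatment prescribed (4.4). Investigators know it.
4. *Is the review masked to cohort or outcome?* No section says so.
5. *Must exclusions be reported by cohort, or the analysis repeated with them kept in?* No section asks for either.

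**Illustration**

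The protocol gives no sample size, response rate or effect size, so there is no figure of its own to reproduce. Cohort sizes, response rates and the pattern of removal below are all assumptions. The test is the protocol's for categorical outcomes (Pearson chi-square, two-sided 0.05), equivalent to

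z = (pA − pB) / √[p(1 − p)(1/nA + 1/nB)], with p the pooled proportion.

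Removing k non-responders from a cohort of n with x responders changes its rate from x/n to x/(n − k).

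*(a) Shift in the estimate.* Two cohorts of 100, both with 60 responders; k non-responders leave one and k responders leave the other.
- k = 5: 60/95 = 63.2% against 55/95 = 57.9%, a difference of 5.3 points. Pooled p = 115/190 = 0.605; standard error 0.071; z = 0.74; p-value about 0.46.
- k = 10: 60/90 = 66.7% against 50/90 = 55.6%, a difference of 11.1 points. Pooled p = 110/180 = 0.611; standard error 0.073; z = 1.53; p-value about 0.13.

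Neither is significant, although the removal is as adverse as possible for its size.

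*(b) False-positive rate.* No true difference, 50% response in both cohorts, and a fixed share of one cohort removed, all non-responders (200,000 simulated studies per cell):

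| Per cohort | 0% removed | 2% | 5% | 10% |
|---|---|---|---|---|
| 100 | 5.66% | 5.75% | 6.70% | 12.90% |
| 200 | 5.06% | 5.52% | 8.49% | 19.97% |
| 300 | 5.16% | 6.18% | 10.22% | 27.00% |

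*(c) Removals needed to create significance between cohorts with identical 50% response.*
- Non-responders from one cohort only: 23 of 100, 35 of 200 (17.5%), 43 of 300 (14.3%), 57 of 500 (11.4%).
- Non-responders from one and responders from the other, per cohort: 13 of 100, 19 of 200 (9.5%), 24 of 300 (8.0%), 31 of 500 (6.2%).

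*(d) Removals needed to lose significance*, taking non-responders from the lower cohort.
- 120/200 against 100/200 has p = 0.044. One removal gives 100/199 and p = 0.0503.
- 180/300 against 150/300 has p = 0.014. Twelve removals give 150/288 and p = 0.053.

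A handful of selective removals matters only when a result is already near the threshold. Creating a difference from nothing takes many more.

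**The case against.** **Existing procedure.** The decision is joint with statisticians, passes through a review report and meeting, and precedes a lock that five roles sign. An SAP that is not at hand may define analysis sets. This does make casual case-picking harder. But sign-off is not masking, and the problem is not missing detail: 4.7 itself leaves the criteria open until review, so an SAP with a closed list would conflict with it.

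**What reviewers know.** A reader might infer that everyone at the review knows outcomes by cohort. The protocol does not say so. It says that clinicians collect the data and is silent on what the statistician sees. Several outcomes are also not clinician ratings (diary temperature, RNA, blood counts). What the protocol supports is that investigators know the treatment and that no masking of the review is described.

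**Section 9.1.1.** A reader might infer a flat contradiction. Section 9.1.1 places its control mainly in design and implementation, and the sentence most naturally concerns which patients doctors register; 4.7 acts later. The two can coexist, although open-ended exclusion brings back a selection step that 9.1.1 is meant to keep out.

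**Reach and permanence.** A reader might infer that every comparison is damaged beyond recovery. Section 4.7 does not say which data set it governs, and nothing says that excluded records are deleted. They could be restored in a sensitivity analysis, though the protocol does not ask for one.

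**Unblinding wording.** The emergency-unblinding text in 7.5-7.6 might suggest that a blind protects the review. It concerns adverse events, sets up no blind, and is no part of this point.

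**The numbers.** They assume purely selective removal. At 2% removal the false-positive rate barely moves. This stands in full: the figures show the mechanism, not an expected bias.

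**Conclusion.** The concern holds as a defect in a stated rule. Section 4.7(3)-(4) permits enrolled cases to be excluded on grounds not written down until the data are in, by people who include investigators aware of treatment, with no masking of the review. Exclusions could depend on cohort and response, and adjusting the retained cases would not correct the resulting bias.

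The size cannot be stated. It depends on how many cases are excluded and how selectively, and the protocol gives neither a limit nor a sample size. Under the assumed 200 per cohort, 50% response and one-sided removal of non-responders, the false-positive rate runs from 5.5% at 2% removed to 20.0% at 10%. Few or unselective exclusions would do little harm. The documents do not show that selective exclusion will happen.

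**What to change.** Delete 4.7(3) and 4.7(4) and replace them with a closed list set before any outcome data are reviewed: eligibility not met on D0 information, no consent, or no post-enrolment data at all.

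- Have eligibility exclusions decided by people without access to outcomes, and without the cohort label except where inclusion criterion (3), the match between prescribed treatment and group, cannot be judged without it.
- Apply the no-post-enrolment-data rule mechanically. It cannot be read from a D0 listing and needs no judgement.
- Keep all other enrolled patients in the main analysis.
- Report exclusions by cohort with reasons.
- Move any further removals to a sensitivity analysis.
- Align 8.6 with this, so that the review meeting applies the list and does not extend it, and make 9.1.1 consistent with it.

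The cost is a wording change and one restricted listing, provided that it is done before data review. The downside is that some messy cases stay in the main analysis; the sensitivity analysis shows whether they matter.
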